8.2.3.3. Fraction Absorbed (Fa)

8.2.3.3.1. Urine Parameters

Following urine parameters will be calculated following single dose administration of a microtracer dose of [^{14}C] PF-06865571 (oral and IV administration). Residual ^{14}C levels from Period 1 will be accounted for using an appropriate method, based on AMS principles and methodology.

Parameter	Definition	Method of Determination
$\text{Total } ^{14}\text{C}_\text{Urine_PO}$	Total radioactivity excreted into the urine postdose following oral administration of [^{14}C]PF-06865571 microtracer dose	Sum of [^{14}C urine concentration \times sample volume] for each collection interval
$\text{Total } ^{14}\text{C}_\text{Urine_IV}$	Total radioactivity excreted into the urine following IV administration of [^{14}C]PF-06865571 microtracer dose	Sum of [^{14}C urine concentration \times sample volume] for each collection interval
$\%^{14}\text{C}_\text{Urine_PO}$	Percent of the radioactive dose administered that is excreted in the urine following oral administration	$\text{Total } ^{14}\text{C}_\text{Urine_PO}/^{14}\text{C Dosepo} \times 100$ Where $^{14}\text{C Dosepo}$ is the dose of ^{14}C following oral administration of [^{14}C]PF-06865571
$\%^{14}\text{C}_\text{Urine_IV}$	Percent of the radioactive dose administered that is excreted in the urine following IV administration	$\text{Total } ^{14}\text{C}_\text{Urine_IV}/^{14}\text{C Doseiv} \times 100$ Where $^{14}\text{C Doseiv}$ is the dose of ^{14}C following IV administration of [^{14}C]PF-06865571

Total urine ^{14}C amounts, percent ^{14}C dose will be listed by treatment (oral in Period 1 and IV in Period 2) and summarized using descriptive statistics.

8.2.3.3.2. Calculation of Fa

Fa will be estimated as the ratio of the adjusted geometric means of % of administered radioactive dose excreted into the urine following oral and IV administration of [^{14}C]PF-06865571 microtracer dose over the same collection time (up to 48 hours post dose) in Periods 1 and 2, respectively:

$$\text{Fa} = [\%^{14}\text{C}_\text{Urine_PO}/\%^{14}\text{C}_\text{Urine_IV}]$$

Geometric mean ratio and 90% confidence interval: Natural log transformed % Total ^{14}C in Urine from Period 1 and Period 2 will be analyzed using a mixed effect model with treatment as a fixed effect and participant as a random effect. Estimates of the adjusted (least squares) mean differences (Test-Reference) and the corresponding 90% CI will be obtained from the model. The adjusted mean differences and 90% CIs for the differences will be exponentiated to provide estimates of the ratio of adjusted geometric means (Test/Reference) and 90% CI for the ratio. Total ^{14}C _Urine_IV is the Reference formulation and Total ^{14}C _Urine_PO is the Test formulation.

Theoretically Fa would be expected to be greater than F. In the event that F is estimated to be greater than Fa, the greater of the 2 values will be used to represent the fraction of PF-06865571 absorbed. PF-06865571 will be considered highly permeable if either F or Fa is greater than 0.85.

PK parameters will be summarized by treatment and analyte as specified in Table 2.

Table 2. PK Parameters to be Summarized Descriptively

Matrix	Parameter	Summary Statistics
Plasma	AUC _{last} , AUC _{last(dn)} , AUC _{inf} , AUC _{inf(dn)} , C _{max} , C _{max(dn)} , F, [CL/F (oral) or CL (IV)] and [Vz/F (oral) or V _{ss} (IV)]	N, arithmetic mean, median, cv%, standard deviation, minimum, maximum, geometric mean and geometric cv%.
Plasma	T _{max}	N, median, minimum, maximum.
Plasma	t _{1/2}	N, arithmetic mean, median, cv%, standard deviation, minimum, maximum.
Urine	Total ^{14}C Urine PO, Total ^{14}C Urine IV, % ^{14}C Urine PO, % ^{14}C Urine IV, Fa	N, arithmetic mean, median, cv%, standard deviation, minimum, maximum.

Box and whisker plots for individual participant parameters (AUC_{inf(dn)}, AUC_{last(dn)}, C_{max(dn)}, % ^{14}C urine PO, and % ^{14}C urine IV) be presented and overlaid with geometric means.

Supporting data from the estimation of t_{1/2}, and AUC_{inf} will be listed by analyte: terminal phase rate constant (k_{el}); goodness of fit statistic from the log-linear regression (r²); the percent of AUC_{inf} based on extrapolation (AUC_{extrap%}); and the first, last, and number of time points used in the estimation of k_{el}. This data may be included in the clinical study report.

Presentations for PK (plasma, where possible) concentrations by analyte will include:

- A listing of all concentrations sorted by participant id and nominal time postdose for each analyte, route of administration and treatment, separately. The listing of concentrations will include the actual times. Deviations from the nominal time will be given in a separate listing.
- A summary of concentrations by nominal time postdose (produced separately for each analyte), where the set of statistics will include n, mean, median, standard deviation, coefficient of variation (cv), minimum, maximum and the number of concentrations above the lower limit of quantification.
- A plot (on both linear and semi-log scales) of median PK and radioactivity concentrations against nominal time postdose (based on the summary of concentrations by time postdose), where the median concentration-time profiles for plasma PF-06865571 PK (Period 1), and plasma radioactivity (Period 1) will be presented together on the same plot.
- A plot (on both linear and semi-log scales) of median PK and radioactivity concentrations against nominal time postdose (based on the summary of concentrations by time postdose), where the median concentration-time profiles for plasma PF-06865571 PK (Period 2), and plasma [¹⁴C] PF-06865571 (Period 2) will be presented together on the same plot where both have been dose-normalized (by oral and IV dose, respectively). The dose-normalization will be calculated by programming using raw concentrations and the actual doses administered.
- Plots (on both linear and semi-log scales) of individual concentrations against actual time postdose by participant. Concentration time plots for analytes PF-06865571 (Period 1) and total radioactivity (Period 1) will be presented together on the same plot. In a separate figure, the analytes PF-06865571 (Period 2) and [¹⁴C]PF-06865571 (Period 2), where both have been dose-normalized (by programming using raw concentrations and the actual doses administered), will be presented together on the same plot.

For summary statistics, median and mean plots by sampling time, the nominal PK sampling time will be used, for individual participant plots by time, the actual PK sampling time will be used.

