4.2. Scientific Rationale for Study Design

This study will investigate the ADME of $[^{14}\text{C}]$ PF-06865571 and characterize plasma, fecal and urinary radioactivity and identify any metabolites, if possible, of $[^{14}\text{C}]$ PF-06865571 in male participants (obtained from Periods 1 and 2). A 2-period design is being used to minimize variability and enable within -participant comparison of the urinary excretion of radioactivity with both routes for the estimation of Fa. Only male participants will be enrolled to also minimize variability. Only nonsmokers will be enrolled to minimize any potential effect on metabolism by smoking. In addition, this study will provide a better understanding of the PK disposition of PF-06865571 by obtaining IV clearance and delineating the extent of oral absorption (F and Fa), further assisting with BCS classification assessment for PF-06865571. This information will support the further formulation development. Oral dosing will be administered with a meal as food has been shown to significantly increase exposures of PF-06865571 and mimics how PF-06865571 is being administered in the clinical program.

Period 2 of this study will enable assessment of F for PF-06865571. F will provide information on the amount of PF-06865571 reaching the systemic circulation. Determination of the Fa (obtained from Periods 1 and 2) will provide information on the fraction of the total PF-06865571 dose absorbed, regardless of the fate of that dose after absorption (ie, metabolism, degradation, etc). Since F is dependent on Fa, Fg and Fh, characterization of

both F and Fa will enable determination of the first pass effect. Therefore, the study will aim to characterize both F and Fa.

In order to achieve sufficient bioanalytical sensitivity for the microtracer dose and differentiate the plasma concentrations resulting from the radiolabeled IV dose and those resulting from the oral dose, an ultra-sensitive AMS method will be used to quantify plasma concentrations of radiolabeled parent drug as well as total ^{14}C derived from the microtracer dose based on measurement of ^{14}C .⁸ PF-06865571 will be considered highly permeable if either F or Fa is greater than 0.85 (as per BCS guidance).⁹

CCI

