9.2. Sample Size Determination

A sample size of 6 male participants has been chosen based on the industry standard sample size for ADME Mass Balance studies and radiolabeled tracer studies. This sample size was not chosen based on any empirical data or hypothesis testing criteria.

Participants who withdraw from the study, for non-safety reasons, may be replaced if the number of participants with evaluable data is less than 4.

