- Geometric Mean Ratio and 90% confidence interval: Natural log transformed % Total ^{14}C in Urine from Period 1 and Period 2 will be analyzed using a mixed effect model with treatment as a fixed effect and participant as a random effect. Estimates of the adjusted (least squares) mean differences (Test-Reference) and the corresponding 90% CI will be obtained from the model. The adjusted mean differences and 90% CIs for the differences will be exponentiated to provide estimates of the ratio of adjusted geometric means (Test/Reference) and 90% CI for the ratio. Total ^{14}C _Urine_IV is the Reference formulation and Total ^{14}C _Urine_PO is the Test formulation.

Theoretically F_a would be expected to be greater than F . In the event that F is estimated to be greater than F_a , the greater of the 2 values will be used to represent the fraction of PF-06865571 absorbed. PF-06865571 will be considered highly permeable if either F or F_a is greater than 0.85 (as per BCS guidance).⁹

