4.2. Statistical Decision Rules

No decision rules are required.

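### Does the highly permeable label (F or Fa above 0.85) need its confidence intervals and its Fa summary written into the rule?

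*SAP*

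**What the plan says.** SAP 8.2.3.3.2 contains four statements that bear on this point.

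- The estimator: "Fa will be estimated as the ratio of the adjusted geometric means of % of administered radioactive dose excreted into the urine", oral over IV. A 90% confidence interval from the mixed model on the log scale follows in the next paragraph. SAP 8.2.3.2 treats F in the same way, using dose-normalised AUC from Period 2.
- The rule for a reversal: if F is estimated above Fa, "the greater of the 2 values will be used to represent the fraction of PF-06865571 absorbed".
- The label: "PF-06865571 will be considered highly permeable if either F or Fa is greater than 0.85". Protocol 4.2 and 9.4.2.1.3.2 carry the same criterion and attribute it to BCS guidance.
- Table 2, which lists descriptive summaries. The urine row, which includes Fa, has "N, arithmetic mean, median, cv%, standard deviation, minimum, maximum". The plasma row that includes F also has the geometric mean and geometric cv%.

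Elsewhere, SAP 4.1 and protocol 9.1 say that no hypothesis is tested, and SAP 4.2 says "No decision rules are required". Protocol 9.2 sets six participants by convention and adds: "This sample size was not chosen based on any empirical data or hypothesis testing criteria". Protocol 4.2 describes the use of F and Fa as "further assisting with BCS classification assessment for PF-06865571" and supporting formulation work.

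**The concern.** A threshold call from four to six men looks like a decision rule in a plan that says it has none. The label sentence gives the planned intervals no role and does not say that the label is only descriptive. It also does not repeat which Fa is compared with 0.85, and Table 2 prints an arithmetic mean and a median of individual Fa without the geometric mean that would match the model. If F came out above Fa, the larger value would stand for the fraction absorbed, and no discussion of the conflict is asked for.

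The label feeds a BCS assessment. A reader who saw only the label could miss that the estimate is imprecise, or that another Fa figure in the tables lies on the other side of 0.85.

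**Working it through.** **Inputs.** From the documents: cut-off 0.85; six enrolled, with at least four evaluable intended; two-sided 90% intervals. The documents give no variability for F or Fa, so the SD of the individual log ratio (s) is assumed to lie between 0.05 and 0.35. The true values below are also assumed. The plan has no precision or power figure to reproduce.

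**1. How noisy is the label?** With complete data the mixed-model estimate equals the geometric mean of the individual ratios, so SE = s/√n on the log scale. Considering Fa alone:

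- P(label wrong) = Φ(−|ln(0.85/true Fa)| / SE), with ln(0.85/0.80) = 0.0606 and ln(0.90/0.85) = 0.0572.
- 90% interval around an estimate of 0.86 = 0.86 × exp(±2.015 × SE), where 2.015 = t(0.95, 5 df).

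| s | SE (n=6) | Given wrongly, true Fa 0.80 | Withheld wrongly, true Fa 0.90 | 90% CI at 0.86 |
|---|---|---|---|---|
| 0.05 | 0.020 | 0.1% | 0.3% | 0.83–0.90 |
| 0.10 | 0.041 | 7% | 8% | 0.79–0.93 |
| 0.15 | 0.061 | 16% | 18% | 0.76–0.97 |
| 0.25 | 0.102 | 28% | 29% | 0.70–1.06 |
| 0.35 | 0.143 | 34% | 34% | 0.64–1.15 |

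At n=4 both errors run from about 1% (s = 0.05) to about 37% (s = 0.35). The noise is confined to a band around the cut-off. At n=6 the error exceeds 20% only for true Fa within 0.85 × exp(±0.842 × SE): 0.81 to 0.90 at s = 0.15, and 0.75 to 0.96 at s = 0.35.

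**2. Does taking the larger value matter?** Protocol 4.2 treats F as Fa reduced by gut and hepatic first-pass loss, so F is a lower bound on Fa, and an F estimate above Fa is itself evidence about absorption. For the label, asking whether either value exceeds 0.85 is the same as asking whether the larger one does, so the reversal rule adds nothing. For size, take true Fa 0.80, true F 0.60, n=6, s = 0.35 and independent estimates. P(F estimate > Fa estimate) = Φ(−ln(0.80/0.60) / (√2 × 0.143)) = Φ(−1.42), about 8%. P(F estimate > 0.85) = Φ(−ln(0.85/0.60) / 0.143) = Φ(−2.44) = 0.7%, which adds about 0.5 percentage point to the error. The effect is large only if F is close to Fa: with both truly 0.80, the label would be given in 1 − (1 − 0.34)², about 56% of trials at s = 0.35. The either/or form is the guidance criterion that the protocol cites and is not in question here.

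**3. Which Fa is compared with 0.85?** The section opens by defining Fa as the ratio of adjusted geometric means. The label comes later in the same section and uses the same symbol, and the sentence before it speaks of estimated values. Table 2 follows and is a table of descriptive summaries. The text therefore points to one Fa. If someone used the Table 2 arithmetic mean instead, it would exceed the geometric mean by about (s²/2) × (n−1)/n: 0.0113 × 5/6 = 0.9% at s = 0.15, and 0.0613 × 5/6 = 5% at s = 0.35. By simulation at n=6 with true Fa 0.80 to 0.84, the two lie on opposite sides of 0.85 in about 1.5% to 4% of trials at s = 0.10, and about 4% to 14% at s = 0.15 to 0.35. At true Fa 0.70 and s = 0.15 the figure is 0.06%.

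**4. What would added wording change?** Calling the label descriptive, naming the ratio and printing the intervals beside it would leave the cut-off, the estimates and n alone, so every rate in step 1 stays the same. Requiring the lower 90% limit to exceed 0.85 would change the rates. At n=6 it would need an estimate of 0.85 × exp(2.015 × SE): 0.92 at s = 0.10, 0.96 at s = 0.15 and 1.13 at s = 0.35. The last is out of reach for a fraction, so such a rule would not suit this study.

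**The case for a change.** The best case for a change is that it costs almost nothing: a few sentences and one table statistic, with no new data and no harder criterion. In return, a label with regulatory use would always be read with its uncertainty and traced to one estimate. SAP 4.2 would no longer seem to deny a rule that appears four sections later.

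Parts of this stand. The label sentence does omit the intervals, and Table 2 does omit the geometric mean for Fa while giving it for F.

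The rest does not carry. The intervals are already planned, the one for Fa in the paragraph just above the label, and SAP 8.1 gives them the role of showing precision. F and Fa each have their own estimate, interval and Table 2 entry, so neither disappears when the larger is used; explaining a reversal belongs in the study report. SAP 4.2 sits under hypotheses, in a study that tests none and whose size was not set for testing. A cut-off taken from BCS guidance is a pharmaceutics convention and does not contradict it. The missing geometric mean can largely be recovered, because the planned box plots overlay geometric means on the oral and IV urine percentages, and with complete data their ratio is the model-based Fa.

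**Conclusion.** No change to the plan is needed. Followed as written, it yields the same F, Fa, 90% intervals and label as it would with the extra wording. The charge that the Fa summary is unnamed fails on the section's own definition, and the charge that the other value would be lost when F exceeds Fa fails because both are reported in any case.

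The misclassification rates are real but conditional. They rest on assumed SDs and true values, run from about 0.1% to 37% across the cases shown for Fa alone at true values of 0.80 and 0.90, and matter only near 0.85. They reflect a study of four to six men, which protocol 9.2 openly sets by convention, and no rewording of the label would reduce them. The primary endpoints are untouched.

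What remains is a reporting preference: showing the intervals next to the label, and adding a geometric mean for Fa to Table 2. A report author can do both from planned output. Even if the sponsor chose to write them down, the SAP alone would be enough. Protocol section 9 lets the SAP modify the outlined analyses and calls for an amendment only for major changes to primary endpoints, and F and Fa are secondary.

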8.3. Safety Analysis

A set of summary tables will be produced to evaluate any potential risk associated with the safety and toleration of administering PF-06865571.

8.3.1. Treatment and Disposition of Participants

Participant evaluation groups will show end of study participant disposition and will show which participants were analyzed for pharmacokinetics, as well as for safety (adverse events and laboratory data). Frequency counts will be supplied for participant discontinuation(s).

Data will be reported in accordance with the sponsor reporting standards.

8.3.2. Demographic and Clinical Examination Data

A break-down of demographic data will be provided for age, race, weight, body mass index, and height. Each will be summarized as 'All Participants' in accordance with the sponsor reporting standards.

8.3.3. Discontinuation(s)

Participant discontinuations, and/or temporary discontinuations due to adverse events will be detailed and summarized.

Data will be reported in accordance with the sponsor reporting standards.

8.3.4. Adverse Events

Adverse events will be reported in accordance with the sponsor reporting standards.

8.3.5. Laboratory Data

The baseline measurement is the last predose measurement taken prior Period 1, Day 1 dose.

Laboratory data will be summarized and listed in accordance with the sponsor reporting standards.

8.3.6. Vital Signs Data

Vital Signs data will be databased and available upon request.

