2.2.3. Tertiary/Exploratory Objectives

- *To characterize cumulative rate of excretion of total radioactivity in urine and feces over time following administration of a single oral dose of [¹⁴C] PF-06865571.*
- *To quantify plasma PK parameters of PF-06865571 in plasma following administration of a single oral dose of unlabeled PF-06865571.*

[REDACTED]

- *To evaluate the safety and tolerability of PF-06865571, administered as a single oral dose of [¹⁴C] PF-06865571 or a single oral dose of PF-06865571 followed by administration of a single IV microtracer of [¹⁴C] PF-06865571.*

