6.5. Safety Endpoints

An adverse event is considered a treatment emergent if the event started during the effective duration of treatment.

Events that occur in a non-treatment period (for example, Washout or Follow-up) will be counted as treatment emergent and attributed to the previous treatment taken.

The following data are considered in standard safety summaries (see protocol for collection days and list of parameters):

- *adverse events*;
- *laboratory data*.

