8.3.7. ECG Data

ECG data will be databased and available upon request.

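### The SAP plans no output for vital signs or 12-lead ECG, although the protocol names both as safety endpoints and promises to describe their abnormalities

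*SAP*

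**What the plan says.** **Protocol.** Section 3 lists four endpoints for the tertiary/exploratory safety and tolerability objective: adverse event monitoring, clinical laboratory measurements, vital signs and 12-lead ECG. Section 9.4.4 says that laboratory, ECG, blood pressure and pulse rate abnormalities of possible clinical concern will be described, and that sentence carries no qualifier. A separate sentence there says safety data will be tabulated or graphed and summarized where that is appropriate. The same section exempts ECG and vital-sign data collected at screening for eligibility from required reporting.

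**SAP.** Section 2.2.3 keeps the objective, which opens "To evaluate the safety and tolerability of PF-06865571, administered as a single oral dose of". Section 6.5 introduces its list with "The following data are considered in standard safety summaries", and the list has two entries, adverse events and laboratory data. Section 8.3.1 uses the same pair when it says disposition will show "which participants were analyzed for pharmacokinetics, as well as for safety (adverse events and laboratory data", where the bracket closes. Sections 8.3.4 and 8.3.5 then plan output: "Adverse events will be reported in accordance with the sponsor reporting standards" and "Laboratory data will be summarized and listed in accordance with the sponsor reporting standards". Sections 8.3.6 and 8.3.7 do not: "Vital Signs data will be databased and available upon request" and "ECG data will be databased and available upon request". Section 8.3.8 lists no other safety data.

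**The concern.** The SAP states a rule for vital signs and ECG that does not meet what the protocol undertakes. Its two sections on these data name no table, listing, figure or narrative. They also do not invoke the sponsor reporting standards, which the SAP does for adverse events and laboratory data.

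A report written exactly to the SAP could be complete with nothing planned on two named safety endpoints. An ECG, blood pressure or pulse rate value that met a concern criterion but was not recorded as an adverse event would be described only if someone asked for the data. What is at stake is completeness of reporting for an exploratory safety objective, in the first study to give this radiolabelled compound orally and intravenously (protocol 2.3). No data are lost.

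**Working it through.** No figure in the plan is in dispute, so the main check is to set the two documents side by side.

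| Item | Protocol | Output planned in SAP |
|---|---|---|
| Adverse events | endpoint (section 3) | yes (6.5, 8.3.4) |
| Laboratory data | endpoint; abnormalities to be described (section 3, 9.4.4) | yes, summarized and listed (6.5, 8.3.5) |
| Vital signs | endpoint; blood pressure and pulse rate abnormalities to be described | none (8.3.6) |
| 12-lead ECG | endpoint; abnormalities to be described | none (8.3.7) |

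**Counts.**
- Endpoints without planned output: 4 − 2 = 2 of 4.
- Kinds of abnormality to be described: 4 (laboratory, ECG, blood pressure, pulse rate). Laboratory is plausibly covered by the summaries and listings in SAP 8.3.5, which leaves 4 − 1 = 3 without planned output.

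**How much data is involved.** As extracted, the Schedule of Activities shows three scheduled in-house readings per completer: Day 1 hour 0 in Period 1, Day 1 hour 0 in Period 2, and Period 2 discharge. Footnote letters in the table are partly lost, so the discharge reading is inferred from the footnotes on Period 2 discharge. With 6 completers:
- 3 × 6 = 18 ECGs and 18 vital-sign sets;
- of these, 2 × 6 = 12 of each come after the Period 1 dose.

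Unscheduled, repeat, early-termination and replacement readings would be additional.

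**How informative the scheduled readings are.** Protocol 2.2.2.2 gives a mean half-life of 1.5 to 5.2 h and a median Tmax of 1.5 to 4 h after single oral doses with food. I assume the same half-life range applies after IV dosing. Elapsed half-lives = hours since dose ÷ half-life.
- Discharge, 48 h after the IV dose: 48/5.2 = 9.2 to 48/1.5 = 32.0.
- Discharge, 48 + 3 = 51 h after the Period 2 oral dose (protocol 6.1.1 gives the IV dose 3 h later): 51/5.2 = 9.8 to 51/1.5 = 34.0.
- Period 2 hour 0, at least 8 × 24 = 192 h after the Period 1 dose: 192/5.2 = 36.9 or more.

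No scheduled post-dose reading therefore falls near Tmax. This limits what formal summaries could show and supports a short listing.

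**The case against.** **The SAP is allowed to differ, and probably meant to.** Protocol section 9 lets the SAP modify the outlined analyses and requires an amendment only for major changes to primary endpoints or their analyses. SAP 6.5, 8.3.1, 8.3.6 and 8.3.7 all point the same way, which looks like a choice. A reader might infer a breach or an oversight, and the documents support neither. What stands is narrower: the visible SAP text does not present this as a departure from protocol 9.4.4 or give a reason.

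**Presentation is required only where appropriate.** That qualifier attaches to tabulation and summary, and with readings so far from Tmax it is a fair reason to omit summary tables. It does not attach to the sentence promising that abnormalities will be described. The screening exemption in 9.4.4 also suggests that in-study readings were not meant to be exempt. Protocol 9.4.4 provides for review and summary during the study for participant safety, and a short account in the study report could meet the commitment, but the SAP does not plan one.

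**Important findings are caught elsewhere.** ECG and vital-sign results the investigator considers clinically significant are adverse events (protocol 10.3.1), and the SAP reports those. ECG or vital-sign changes can lead to stopping study intervention (protocol 7.1), and SAP 8.3.3 covers discontinuations due to adverse events. This stands and limits severity. It does not cover a value that meets a concern criterion but is not judged an adverse event.

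**Appendix 7 should not be used to size the gap.** A reader might note that 6 + 11 = 17 of its 24 ECG findings (17/24 = 71%) are headed as ones that only may qualify as adverse events or as serious ones, and infer that most would go unreported. The documents do not support that. Eleven of the 17 sit under a heading that leaves open seriousness; only 6 of 24 (25%) sit under one that questions adverse event status. The appendix calls its list alerts to the investigator and study team, and a count of list entries is not an expected number of events.

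**Conclusion.** The point holds as a minor inconsistency between protocol and SAP. Two of four named safety endpoints, and the promised description of ECG, blood pressure and pulse rate abnormalities, have no planned output, and the departure is neither acknowledged nor justified. Primary endpoints, F, Fa and the other secondary results are unaffected.

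Two further inferences should be resisted. Laboratory abnormalities are not part of the gap. The lack of an ECG or vital-sign baseline is not a separate defect: SAP 8.3.5 defines one for laboratory data only, and none is needed elsewhere while no output is planned.

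The conclusion rests on the legible text. SAP 8.3.11 is blacked out, but vital signs and ECG have their own readable sections, so it is unlikely to change the finding. The general mention of safety summary tables at the start of SAP 8.3 does not override those sections. The reading counts assume 6 completers and the schedule as extracted.

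**What to change.** Add vital signs and 12-lead ECG to SAP 6.5 and 8.3.1. In 8.3.6 and 8.3.7, replace release on request with:

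1. A by-participant listing of in-study readings, scheduled and unscheduled, shown against baseline. Define baseline as SAP 8.3.5 does for laboratory data: "The baseline measurement is the last predose measurement taken prior Period 1, Day 1 dose".
2. A short description of any values meeting concern criteria. For ECG, use the criteria already in protocol 8.2.3 and Appendix 7, and name the criterion met, because the QTcF thresholds in the two places are not identical. For blood pressure and pulse rate, cite the sponsor standard if one exists; otherwise fix the criteria before database release.

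Summary and change-from-baseline tables are not needed with six participants. A sentence acknowledging and justifying the departure from protocol 9.4.4 would be cheaper and would cure the silence, but it would not deliver the promised description.

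The cost is SAP wording and a few short outputs from data already databased, plus the work of citing or fixing the blood pressure and pulse rate criteria. No new data are collected and study conduct does not change.
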